Protocol Study ID: NN8640-4787 UTN: U1111-1294-5941 EU PAS No.: Pending

CONFIDENTIAL

Date: Version: Status: Page: 17 July 2024 | **Novo Nordisk**3.0
Final
1 of 48

Protocol

Study ID: NN8640-4787

REAL 10

A Non-Interventional, Observational, Registry-Based Study to Investigate Long-Term Safety and Clinical Parameters of Somapacitan Treatment in Paediatric Patients with Growth Hormone Deficiency During Routine Clinical Practice.

Non-interventional (NIS) post authorisation safety study (PASS)

Redacted protocol Includes redaction of personal identifiable information only.

This confidential document is the property of Novo Nordisk. No unpublished information contained herein may be disclosed without prior written approval from Novo Nordisk. Access to this document must be restricted to relevant parties.

17 July 2024 | Novo Nordisk Date: CONFIDENTIAL

Protocol Study ID: NN8640-4787 UTN: U1111-1294-5941 EU PAS No.: Pending

Version: Status: Page:

3.0 Final 2 of 48

PASS information

Title	A non-interventional, observational, registry-based study to		
	investigate long-term safety and clinical parameters of somapacitan treatment in paediatric patients with growth hormone deficiency during routine clinical practice.		
Protocol author	, Novo Nordisk A/S		
Protocol version identifier	3.0		
Date of last version of protocol	Not applicable		
EU PAS Register number	Pending		
Active substance	Somapacitan; ATC code: H01AC07		
Medicinal product	Sogroya [®]		
Product reference	EU/1/20/1501		
Procedure number	EMEA/H/C/005030/MEA/005		
Marketing authorisation holder(s)	Novo Nordisk A/S [name]		
Joint Post Authorisation Safety Study (PASS)	No		
Research question and	Primary objective		
objectives	To investigate long-term safety of somapacitan treatment in paediatric patients with growth hormone deficiency (GHD) in the setting of routine clinical practice with special focus on neoplasms and type 2 diabetes mellitus (T2DM).		
	Secondary objective		
	To investigate safety and clinical parameters of somapacitan treatment in paediatric patients with GHD in the setting of routine clinical practice.		
	To compare the occurrence of adverse drug reactions including neoplasms and T2DM in patients treated with somapacitan with historical data from literature (NordiNet® IOS, ANSWER studies and GeNeSIS registry) of paediatric GHD patients treated with daily somatropin.		

PASS post authorisation safety study

PT preferred term

RMP risk management plan
SAE serious adverse event
SAP statistical analysis plan

SAS safety analysis set

SDS standard deviation score
SIR standardised incidence ratio

SOC system organ class

SmPC summary of product characteristic

Protocol Study ID: NN8640-4787 UTN: U1111-1294-5941 EU PAS No.: Pending

CONFIDENTIAL

Date: Version: Status: Page: 17 July 2024 | Novo Nordisk 3.0 Final

7 of 48

T2DM UTN type 2 diabetes mellitus universal trial number
 Protocol
 Date:
 17 July 2024
 Novo Nordisk

 Study ID: NN8640-4787
 Version:
 3.0

 UTN: U1111-1294-5941
 Status:
 Final

 EU PAS No.: Pending
 Page:
 8 of 48

3 Responsible parties

Novo Nordisk A/S will be responsible for the preparation of the protocol.

In this document physician/treating physician refers to the individual overall responsible for entering data from the paediatric patient with growth hormone deficiency (GHD) into the Global registry for novel therapies in rare bone and endocrine conditions (GloBE-Reg).

GloBE-Reg is an international consortium-led registry project owned by the University of Glasgow, with industry partners (including Novo Nordisk A/S), major professional endocrine societies, and patient representatives, collecting real-world data on the safety and clinical parameters of several medicinal products (including somapacitan) in the field of rare bone and endocrine conditions. The data for this study will be drawn from GloBE-Reg.

17 July 2024 | Novo Nordisk Date:

Protocol Study ID: NN8640-4787 Version: 3.0 CONFIDENTIAL UTN: U1111-1294-5941 Final Status: EU PAS No.: Pending 9 of 48 Page:

4 **Abstract**

4.1 Title

A non-interventional, observational, registry-based study to investigate long-term safety and clinical parameters of somapacitan treatment in paediatric patients with growth hormone deficiency during routine clinical practice.

4.2 Milestones

Milestone	Planned date
Start of data collection – First patient first visit (FPFV)	Q4 2024
Last patient first visit – end of study recruitment	5-year recruitment period from Q4 2024
Interim report	Q4 2030 (6 years from start of data collection)
Last patient last visit (LPLV)	Planned to be conducted until Q3 2034
End of data collection – defined as data base lock	Q4 2034
Final report of study results	Q4 2035
Study progress reports	To follow PSUR timelines ^a

^aAnnual progress reports, submitted with PSUR (when applicable).

4.3 Rationale and background

Sogroya[®] (somapacitan) (hereafter only referred to as somapacitan) is a long-acting human growth hormone (hGH) derivative, with a single amino acid substitution in the backbone to which a non-covalent albumin binding moiety has been attached. Somapacitan is intended for once weekly subcutaneous administration with the aim of reducing injection frequency and treatment burden and potentially decreasing the barrier to initiating and/or maintaining replacement therapy in GHD. 1.2 The mechanism of action of somapacitan is via insulin-like growth factor 1 (IGF-I). ^{1,2} Daily growth hormone (GH) injections can be burdensome for paediatric patients and their caregivers, disrupting and interfering with daily life. This could lead to non-adherence to prescribed replacement therapy and suboptimal clinical outcomes. 3,4

As part of the risk management plan (RMP) for somapacitan, this non-interventional, observational, registry-based study is planned to evaluate long-term safety and clinical parameters of somapacitan treatment in paediatric patients with GHD in the setting of routine clinical practice.

The data for this study will be drawn from GloBE-Reg (see Section 9.4). In line with European Medicines Agency (EMA) guidelines (EMA/426390/2021, current version), the GloBE-Reg is an international consortium-led registry project owned by the University of Glasgow, with industry partners (such as Novo Nordisk A/S), major professional endocrine societies, and patient representatives, collecting real-world data on the safety and clinical parameters of several medicinal products (including somapacitan) in the field of rare bone and endocrine conditions.

 Protocol
 Date:
 17 July 2024
 Novo Nordisk

 Study ID: NN8640-4787
 Version:
 3.0

 UTN: U1111-1294-5941
 Status:
 Final

 EU PAS No.: Pending
 Page:
 10 of 48

This registry-based study will only investigate paediatric GHD patients from GloBE-Reg who have been treated with somapacitan.

4.4 Research question and objectives

4.4.1 Primary objective

To investigate long-term safety of somapacitan treatment in paediatric patients with GHD in the setting of routine clinical practice with special focus on neoplasms, medication errors and T2DM.

4.4.2 Secondary objective

- To investigate safety and clinical parameters of somapacitan treatment in paediatric patients with GHD in the setting of routine clinical practice.
- To compare the occurrence of adverse events (AEs), serious adverse events (SAEs), serious adverse drug reactions (serious ADRs) including neoplasms and T2DM in patients treated with somapacitan with historical data from literature (NordiNet® IOS, ANSWER studies and GeNeSIS registry) of paediatric GHD patients treated with daily somatropin.

4.5 Study design

This is a non-interventional, multi-national, single-treatment arm, observational, registry-based study to investigate the long-term safety and clinical parameters of somapacitan in paediatric patients with GHD under routine clinical practice conditions. The study population will consist of at least 400 paediatric GHD patients from the GloBE-Reg registry treated with once-weekly somapacitan who meet the inclusion criteria.

Patients will be treated with commercially available somapacitan according to routine clinical practice at the discretion of the treating physician.

The total duration of the study is planned to be 10 years consisting of a 5-year recruitment period in the GloBE-Reg followed by at least a 5-year follow-up period. The study is planned to be conducted from Q4 of 2024 until Q4 of 2034.

4.6 Population

The study population will consist of at least 400 paediatric GHD patients (both naïve and non-naïve) from the GloBE-Reg registry treated with once weekly somapacitan.

4.6.1 Inclusion criteria

For an eligible patient, all inclusion criteria must be answered 'yes'.

- 1. Treated with commercially available somapacitan according to local practice at the discretion of the physician.
- 2. Primary confirmed diagnosis of GHD as per local practice.
- 3. Male or female below 18 years of age at the time of signing informed consent in the GloBE-Reg.

 Protocol
 Date:
 17 July 2024
 Novo Nordisk

 Study ID: NN8640-4787
 Version:
 3.0

 UTN: U1111-1294-5941
 Status:
 Final

 EU PAS No.: Pending
 Page:
 11 of 48

4.6.2 Exclusion criterion

For an eligible patient, the following exclusion criterion must be answered 'no'.

1. Patients with active malignancy or in treatment for active pre-existing malignancy.

4.7 Variables

For the primary and secondary endpoints, data on the following variables will be extracted from the GloBE-Reg registry.

The number of ADRs from baseline to the EOS will be recorded as primary endpoint. Safety endpoints such as number of AEs, SAEs, serious ADRs, medication errors, incident neoplasm, incident T2DM from baseline (week 0) to EOS will be recorded as secondary endpoints. Additionally, other clinical parameters will also be recorded as secondary endpoints. Safety data will be collected by GloBE-Reg for the registered paediatric patients with GHD.

Incidence rates for neoplasms will be compared to incidence rates published in the combined NordiNET/ANSWER studies. 6-8 Similarly, incidence rates for T2DM will be compared to published results from the GeNeSIS study. 9.10 From both studies, the incidence rates for isolated GHD will be used for the comparison.

4.8 Data Sources

The data for this study will be drawn from GloBE-Reg. .

4.9 Study sample size

The study is planned for the sample size of at least 400 patients (inclusive of both naïve and non-naïve).

4.10 Data analysis

Data from at least 400 paediatric patients with GHD (inclusive of both naïve and non-naïve) will be analysed using safety analysis set (SAS). The number of ADRs from baseline to EOS will be analysed. EOS will differ from patient to patient. AEs, SAEs and serious ADRs during the study period will be summarised by Medical Dictionary for Regulatory Activities (MedDRA) system organ class (SOC) and preferred term (PT). This summary is displayed with number and proportion of patients with at least one event, number of events and event rate (events per 100 patient-years of exposure).

The combined data from NordiNet[®] IOS and ANSWER studies will be used as external comparator for the occurrence of ADRs including neoplasms⁶⁻⁸. Data from the GeNeSIS registry will be used as external comparator for the occurrence of T2DM. ^{9, 10} The aggregated data from isolated GHD from both publications will be used for the comparison.

The standardised incidence ratio (SIR) with a 95% confidence interval will be used as an additional estimate for neoplasms and new-onset T2DM.

A statistical analysis plan (SAP) will be written, including a detailed elaboration of the statistical analyses. The SAP will be finalised before database lock. Data from the registry will be analysed and reported.

17 July 2024 Novo Nordisk Date:

Protocol Study ID: NN8640-4787 Version: 3.0 CONFIDENTIAL UTN: U1111-1294-5941 Status: Final EU PAS No.: Pending Page: 12 of 48

5 Amendments and updates

Amendment or update no	Date	Section of study protocol	Amendment or update	Reason
1	28 February 2024	General update	Update	Following PRAC
		of the protocol		review
2	17 July 2024	General update	Update	Following PRAC
		of the protocol		review

Protocol Study ID: NN8640-4787 17 July 2024 | Novo Nordisk Date: Version: 3.0 CONFIDENTIAL Status:

Page:

Final

13 of 48

UTN: U1111-1294-5941 EU PAS No.: Pending

Milestones 6

Milestone	Planned date
Start of data collection	Q4 2024
End of data collection	Q4 2034
Study progress report	To follow PSUR timelines ^a
Interim report	Q4 2030 (6 years from start of data collection)
Final report of study results	Q4 2035

^aAnnual progress reports, submitted with PSUR (when applicable).

Protocol

Study ID: NN8640-4787 UTN: U1111-1294-5941 EU PAS No.: Pending

CONFIDENTIAL

Date: Version: Status: Page: 17 July 2024 | **Novo Nordisk**3.0
Final
14 of 48

7 Rationale and background

Somapacitan is a long-acting hGH derivative, with a single amino acid substitution in the backbone to which a non-covalent albumin binding moiety has been attached. Somapacitan is intended for once weekly subcutaneous administration with the aim of reducing injection frequency and treatment burden and potentially decreasing the barrier to initiating and/or maintaining replacement therapy in GHD. The mechanism of action of somapacitan is via IGF-I. Daily GH injections can be burdensome for paediatric patients and their caregivers, disrupting and interfering with daily life. This could lead to non-adherence to prescribed replacement therapy and suboptimal clinical outcomes. 3.4

As part of the European marketing authorisation for somapacitan for the treatment of paediatric patients with GHD, Novo Nordisk A/S received a requirement from the Committee for Medicinal Products for Human Use (CHMP) under the European Medicines Agency (EMA) to conduct a non-interventional, observational registry-based study to investigate long-term safety and clinical parameters of somapacitan treatment in paediatric patients with GHD in the setting of routine clinical practice.

As per the RMP, the primary aim of this non-interventional, observational registry-based study is to assess the long-term safety profile of somapacitan with special focus on the important potential risks (neoplasm, T2DM, and medication errors). This post authorisation safety study (PASS) will also provide additional long-term safety information (AEs, SAEs and serious ADRs) and will further substantiate the evaluation of potential risks in relation to treatment with somapacitan.

The secondary aim is to investigate the clinical parameters in patients treated with somapacitan with regards to changes in height velocity SDS, height SDS, IGF-I SDS, and bone age.

To draw clinically relevant conclusions on long-term safety of somapacitan, this study will compare safety data with historical data from literature (NordiNet® IOS, ANSWER⁶⁻⁸ studies and GeNeSIS⁹. 10 registry) of paediatric GHD patients treated with daily somatropin.

Brief description of these external comparators has been outlined below:

NordiNet® IOS (study GHLIQUID-3676) and ANSWER (study HGH-2149)

The NordiNet® International Outcome Study (IOS) and the ANSWER (American Norditropin® Studies: Web Enabled Research) programs were post-marketing non-interventional studies that collected data concerning the treatment management and outcomes of patients, both paediatric and adult, who were prescribed Norditropin® in a real-world setting. The two studies were complementary with common design where NordiNet® IOS covered Europe and Middle East (2006-2016) and ANSWER covered the US (2002-2016). The combined studies enrolled a total of 37,702 paediatric patients with short stature due to different aetiologies of which around 22,000 patients had GHD. The studies included both GH treatment naïve and non-naïve patients. These real-world clinical practice studies of paediatric patients with GHD, treated with Norditropin® supported the long-term effectiveness and safety profile of this treatment in the specified populations. The NordiNet® and ANSWER studies evaluated the safety of GH treatment as frequency and incidence rates of SAEs and/or treatment-related AEs including incidence rates of neoplasms.

17 July 2024 | Novo Nordisk Date:

Protocol Study ID: NN8640-4787 Version: 3.0 CONFIDENTIAL UTN: U1111-1294-5941 Status: Final EU PAS No.: Pending Page:

GeNeSIS - Genetics and Neuroendocrinology of Short Stature International Study

GeNeSIS was an international, observational, open-label and post-authorisation safety study in children with growth disorders covering Canada, France, Germany, Japan, and the US (1999-2015). Data from 11,686 GH-treated paediatric patients, 7,523 with GHD⁹, were analysed for diabetes incidence. Baseline diabetes prevalence was determined from a GH-naïve subgroup. Prevalence and incidence (by SIR) were compared with results from patients aged less than 20 years in the U.S. SEARCH for Diabetes in Youth study. 10

The data for this registry-based study will be drawn from GloBE-Reg (see Section 9.4). In line with EMA guideline on registry-based studies (EMA/426390/2021, current version), GloBE-Reg is an international consortium-led registry project owned by the University of Glasgow, with industry partners (including Novo Nordisk A/S), major professional endocrine societies, and patient representatives. GloBE-Reg collects real-world data on the safety and clinical parameters of several medicinal products (including somapacitan) in the field of rare bone and endocrine conditions.

This registry-based study will only investigate paediatric patients from the GloBE-Reg who have GHD and have been treated with somapacitan.

Additional information on each of the safety concerns to be addressed by this PASS is provided below.

Long term safety

Novo Nordisk A/S has included 'long-term safety' as missing information in the RMP for paediatric GHD.

The paediatric pivotal trial NN8640-4263, included in the submission package, included safety information from subjects with up to one year (52 weeks) of somapacitan exposure (i.e., short term/intermediate term). No safety data for patients with >1 year (52 weeks) of somapacitan exposure were included. Therefore, 'long term safety' is classified as missing information in the RMP and is included as the primary objective in this PASS.

Neoplasms

GH is anabolic and mitogenic, and IGF-I is antiapoptotic. Both hormones can cause proliferation of normal and malignant cells. In general, hGH treatment increases the blood IGF-I levels, but data do not generally support a carcinogenic effect of treatment with GH and there is no established relationship between high blood IGF-I levels and the risk of a malignancy. 12-14

T2DM

Treatment with GH may decrease insulin sensitivity, particularly at higher doses in susceptible patients. Consequently, hyperglycaemia may occur in subjects with inadequate insulin secretory capacity. As a result, previously undiagnosed impaired glucose tolerance and overt T2DM may be unmasked during GH treatment.

Impaired insulin sensitivity is a hallmark of T2DM. This effect of GH has been partly linked to the lipolytic effects of GH resulting in increased plasma levels of free fatty acids, plasma glucose and insulin levels in the hours following injections of hGH. 15, 16

 Protocol
 Date:
 17 July 2024
 Novo Nordisk

 Study ID: NN8640-4787
 Version:
 3.0
 3.0
 Status:
 Final
 Final
 Final
 Final
 Page:
 16 of 48
 17 July 2024
 Novo Nordisk
 Nordisk
 16 of 48
 17 July 2024
 Novo Nordisk
 16 of 48
 17 July 2024
 Novo Nordisk
 17 July 2024
 Novo Nordisk
 18 of 48
 18 of

Medication error

When there are both daily and weekly GH products on the market, there is a risk that the once weekly product might be mistakenly (by the patient/caregiver) administered daily, which could lead to incorrect dose administration rate and overdose.

When patients are used to take their injection daily, there is a risk that this will continue.

No events of medication errors (incorrect dose administration rate) have been reported from completed/ongoing trials for paediatric GHD.

Protocol Study ID: NN8640-4787 UTN: U1111-1294-5941 EU PAS No.: Pending

CONFIDENTIAL

Date: 17 July 2024 Novo Nordisk Version: Status: Page:

3.0

Final

17 of 48

Research question and objectives 8

8.1 **Primary objective**

To investigate long-term safety of somapacitan treatment in paediatric patients with GHD in the setting of routine clinical practice with special focus on neoplasms, medication errors and T2DM.

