9.1.2 Treatment of patients

Patients will be treated with commercially available somapacitan according to routine clinical practice at the discretion of the treating physician. The decision to treat a patient with somapacitan will be made at the treating physician's discretion prior to, and independently from, the decision to include the patient in the GloBE-Reg registry. Novo Nordisk A/S will not provide any products for included subjects during the conduct of the study.

Data collection for the GloBE-Reg registry will happen in conjunction with the patient's usual visits in the clinic. Additionally, optional visits are allowed per local standard of care.

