9.2.2 Inclusion criteria

For an eligible patient, all inclusion criteria must be answered 'yes'.

- 1. Treated with commercially available somapacitan according to local practice at the discretion of the physician.
- 2. Primary confirmed diagnosis of GHD as per local practice.
- 3. Male or female below 18 years of age at the time of signing informed consent in the GloBE-Reg.

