9.7.2.2 Analysis of secondary endpoints

Binary secondary endpoints:

The binary secondary endpoints include:

- Incident neoplasm
- Incident T2DM

Incidence rates will be calculated for both endpoints and compared to aggregated data of incident neoplasms from the combined NordiNET/ANSWER study⁶ and incident T2DM from the GeNeSIS study.⁹ From both studies, the incidence rates for isolated GHD will be used for comparison. The SIR with a 95% confidence interval will be used as an additional estimate for neoplasms and new-onset T2DM.

 Protocol
 Date:
 17 July 2024
 Novo Nordisk

 Study ID: NN8640-4787
 Version:
 3.0
 3.0

 UTN: U1111-1294-5941
 Status:
 Final

Page:

25 of 48

Count-data secondary endpoints:

The analyses of the following secondary endpoints (counted from the baseline (week 0) to the EOS^a) will be done in the same way as the analysis of the primary endpoint:

• Number of AEs

EU PAS No.: Pending

- Number of SAEs
- Number of serious ADRs
- Number of medication errors

Continuous secondary endpoints

For the following secondary endpoints (clinical parameters), the change will be estimated by length of follow up and treatment duration.

- Height velocity
- Change in height velocity SDS
- Change in height SDS
- Change in IGF-I SDS
- Change in bone age

Patients reaching near adult height will be evaluated at EOS only for those who are expected to reach near adult height during the study. Change in height SDS in subjects reaching near adult height will be calculated from baseline (week 0) to EOS.

Note: Near adult height can be defined as height velocity <2 cm/year over the last 9 months and chronological age >16 years (males) or >15 years (females) or bone age >16 years (males) and >15 years (females).

IGF-I SDS will be used to evaluate treatment adherence assuming an increase in IGF-I SDS represents a response to GH treatment.

To deal with patients switching medication in-study and on-treatment analyses will be performed as defined below. The analyses will be repeated separately for GH treatment naïve and non-naïve patients previously receiving other GH treatment as data allows.

In-study

The observation period represents the time frame during which patients are considered to be part of the study, regardless of their adherence to somapacitan treatment. The in-study period starts at the time of informed consent and ends at the date of whichever comes first:

- EOS visit (last visit within the study duration)

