9.9 Limitations of the research methods

Data collection for this study will reflect routine clinical practice rather than mandatory assessments at pre-specified time points. The study captures data in GloBE-Reg from many different regions and settings. As data collection will reflect national, regional, and local differences in routine clinical practice regarding diagnostics, laboratory analyses, and reporting of events, potential issues may arise due to the study design. These issues may result in heterogeneous reporting of specific outcomes and time points for collection. Therefore, it is important to take these differences into account during the interpretation of data.

AEs are collected into GloBE-Reg based on the answer to the below question:

"Since the last recorded clinical encounter in the GloBE-Reg registry, has the patient experienced any untoward medical occurrence (sign, symptom or disease)"

In addition, the physician is responsible for evaluating the seriousness and causality of the AEs.

The safety endpoints are therefore limited to the physician's evaluation of these questions, and due to the secondary collection of data this evaluation cannot be further investigated.

The data source for the study, GloBE-Reg, captures data from many different regions and settings. This leads to a potentially heterogeneous patient population and different local standard of care and data capture, e.g., local differences in diagnostics, laboratory analyses, and reporting of events. This could result in a risk of information bias.

There is a risk of selection bias in the study, affected by the willingness and/or ability of physicians and patients to participate in GloBE-Reg. In addition, any undiagnosed patients will not be able to participate, and the rate of underdiagnosis may vary between regions. This may lead to a selected patient population, which does not accurately reflect the underlying patient population and may result in limited data on certain subgroups.

The long-term follow-up is a strength of this non-interventional study, but also leads to a risk of loss to follow up.

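### Medication errors get one pooled summary although some patients may already be on somapacitan at consent, so a zero count could overstate reassurance about the daily-for-weekly switching error

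*Protocol*

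**What the plan says.** Sections 4.4.1 and 8.1 name medication errors, with neoplasms and T2DM, as a special focus of the primary objective. Section 7 gives two routes to the daily-for-weekly error. One is that both product types are on the market, so that "there is a risk that the once weekly product might be mistakenly (by the patient/caregiver) administered daily". The other is carry-over of habit: "When patients are used to take their injection daily, there is a risk that this will continue". No time window is given for either. The same section adds: "No events of medication errors (incorrect dose administration rate) have been reported from completed/ongoing trials for paediatric GHD".

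On entry and observation time:

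- Section 9.2.2 requires "Treated with commercially available somapacitan according to local practice at the discretion of the physician". It sets no limit on time since the first dose.
- Section 9.1.2 places the treatment decision "prior to, and independently from, the decision to include the patient in the GloBE-Reg registry", again without limiting the gap.
- Section 9.7.2.2 says "The in-study period starts at the time of informed consent". It dates on-treatment time from treatment start, but makes it part of the in-study period.
- Section 9.9 gives the adverse-event question: "Since the last recorded clinical encounter in the GloBE-Reg registry, has the patient experienced any untoward medical occurrence".

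On analysis, Section 9.7.1 pools all patients exposed during the study period. Section 9.7.2.2 says that the analysis of the count endpoints, medication errors among them, "will be done in the same way as the analysis of the primary endpoint". Under Section 9.7.2.1 that means patients with at least one event, number of events, rate per 100 patient-years of exposure, and a Spearman correlation with treatment duration.

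**The concern.** A daily habit can carry over only from the switch onwards, so it is reasonable to expect that part of the risk to be highest early. A child who switched well before consent may have passed that time before observation began, yet still adds a patient and years of follow-up to the denominators. Prior trials reported no such error, so a zero or near-zero count is a realistic outcome here. It could be read as evidence about switching when some of the cohort was never observed during the switch. Early ADRs, which count towards the primary endpoint, are open to the same problem.

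No planned analysis isolates patients observed from first dose. The naïve/non-naïve repeat sorts by earlier other GH: a child on day 1 of somapacitan and one two years into it are both non-naïve. The Spearman correlation uses treatment duration and cannot recover early time that was not observed. The listed subgroups are sex, age, dose, country or region, and Tanner stage.

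**Working it through.** **The plan's own figure.** Table 9-4 gives Wilson 95% limits for an ADR incidence of 2%. Recomputing without continuity correction gives (1.02, 3.90)% at N = 400, against the stated (1.02, 3.89)%. The other rows also agree to within 0.01. The protocol has no precision figure for medication errors.

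**Zero-event limit.** This needs no assumed error rate. With 0 events in n patients, the upper limit of the exact two-sided 95% interval is 1 − 0.025^(1/n).

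| Patients observed from first dose | Upper limit |
|---|---|
| 400 | 0.92% |
| 200 | 1.83% |
| 100 | 3.62% |

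The 400 is from Section 9.5. The 200 and 100 are illustrations, because the protocol does not give the share. GH-naïve patients have no daily habit to carry over, so the number informative for the switching error would be smaller again.

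**Dilution of the proportion.** Assume that a share q of patients make the error, all soon after starting, and that a share f are past that time at consent. For illustration, treat every patient as a switcher. The expected pooled proportion is q(1 − f), and the chance of no event is (1 − q)^(400(1 − f)).

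| f | q = 2%: pooled | q = 2%: expected patients | q = 2%: chance of 0 | q = 1%: chance of 0 |
|---|---|---|---|---|
| 0% | 2.0% | 8 | 0.03% | 1.8% |
| 25% | 1.5% | 6 | 0.2% | 4.9% |
| 50% | 1.0% | 4 | 1.8% | 13.4% |
| 75% | 0.5% | 2 | 13.3% | 36.6% |

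**Dependence on the hazard shape.** Let the rate be r1 for the first w years on somapacitan and r2 afterwards, with T years of follow-up. The pooled rate is [(1 − f)(r1·w + r2(T − w)) + f·r2·T]/T. Assume r1 = 4 per 100 patient-years, w = 0.5, T = 5 and f = 50%.

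| Later rate r2 | Pooled rate, f = 0 | Pooled rate, f = 50% | Ratio |
|---|---|---|---|
| 0 | 0.40 | 0.20 | 0.50 |
| 0.4 | 0.76 | 0.58 | 0.76 |
| 2 | 2.20 | 2.10 | 0.95 |
| 4 | 4.00 | 4.00 | 1.00 |

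The understatement can therefore be a half, a few per cent or nothing, depending on how early the risk falls.

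**The case against.** A reader might infer that the reported error frequency is biased towards zero outright. The documents do not support that:

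- The early window is an inference. Section 7 states none, and its first route to the error is not tied to switching. With a constant hazard the rate is unbiased.
- The share of patients already on treatment at consent is unknown and may be small. Section 9.4 describes a registry that includes people about to start treatment, so entry near the first dose is a described route.
- It goes too far to say that earlier errors are never elicited or that early stoppers never enter. Section 9.4 expects medication-error details to be recorded and does not say that the Section 9.9 question is the only means of capture. The look-back at a first registry encounter is not stated. Section 9.4 also covers people for whom treatment has been considered.
- Section 11.1 defines medication error broadly, including intercepted and potential errors. Only the switching component could be diluted.
- Patients already on treatment serve the long-term aim, since Section 7 names exposure beyond 52 weeks as the gap. Section 9.2.4 keeps eligibility broad on purpose.

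All of this stands and makes the point conditional. A further objection is that table splits belong in the SAP, to which Section 4.10 leaves the detail. That has some force, but the protocol itself fixes the pooled summary and lists the subgroups, and none of these separates patients observed from first dose.

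**Conclusion.** The point holds conditionally, as a cheap improvement rather than a flaw that invalidates the endpoint. The protocol permits entry after somapacitan has started, begins the in-study period at consent and plans a pooled medication-error summary. If the switching error clusters soon after the switch, the pooled proportion and rate understate that component, and a zero count carries less information than 400 patients suggest: an upper limit of 1.83% or 3.62% instead of 0.92% if only 200 or 100 were observed from first dose. The share, the error rate and the hazard shape are all assumptions, so no single size of bias can be claimed. The split is informative whichever shape is true, because without it the data cannot show whether the risk is early.

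**What to change.** In Section 9.7.2.2, keep the overall result and add the following for medication errors and for ADRs:

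1. A split by somapacitan start on or after consent versus before consent.
2. A split by time since somapacitan start, for example 0-3, >3-12 and >12 months.
3. Within patients observed from first dose, a split by prior GH versus GH-naïve. Any statement about the frequency of the switching error should rest on those with prior GH.

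The somapacitan start date is collected (Section 9.3.1), the consent date already defines the in-study period, and GH duration at inclusion is a covariate (Section 9.3.3). The covariate list does not show whether prior GH was daily, so the third split uses any prior GH.

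The cost is some extra programming and wider intervals in the new-user stratum. That loss of precision is a reason to keep the overall result rather than replace it.
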